7.2. Study Drug Discontinuation

Patients should discontinue study drug for any of the following reasons:

- Malignancy, not including local and non-serious basal, squamous cell skin cancer or ductal carcinoma in situ
- Pregnancy
- Anaphylaxis, anaphylactoid or serious hypersensitivity reaction
- Use of any medication, intended to chronically treat psoriasis (refer to [Section 6.12.2](#)), other than those documented at screening
- Adverse event which in the opinion of the investigator or SMC precludes the patient from safely continuing in the study
- Patient is noncompliant with study requirements

The date and reason for discontinuation should be documented in the eCRF.

Patients who discontinue study drug should continue in the study to complete all scheduled assessments.

Those patients who are unwilling or unable to complete all remaining study assessments should return to the study site 2 weeks (\pm 7 days) after the date study drug was discontinued, to complete the early study termination assessments (ET Visit).

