8.3.1.4. Reporting of SAEs

Any AE that is serious and that occurs during the course of the study from the signing of the informed consent to end of study for each patient must be reported by the Investigator to the following:

- The Sponsor (or designee) and study monitor within 24 hours of the Investigator becoming aware of the event (expedited reporting).
- The investigation site's IRB/IEC by the Investigator in accordance with their regulations.

Initial Notification of a Serious Adverse Event (SAE)

Pharmacovigilance must be informed in writing 24 hours from the time the site investigational team first becomes aware of the event using the EDC system, as well as completing a paper SAE report forms.

A paper SAE form including a written, narrative description of any SAE must be sent via email (preferred) or fax within 24 hours after awareness of the event to:

Email: [REDACTED]

Phone: [REDACTED]

Fax: [REDACTED]

Paper SAE forms must be retained in the Investigator Site File.

In addition to reporting the SAE in the EDC and emailing the paper form, the local CRA and the Medical Monitor must be alerted via phone.

As further information regarding the SAE becomes available, follow-up information should be documented as an update using the paper SAE form. Follow-up information should be reported with 24 hours of awareness.

Related SAEs must be collected and reported regardless of the time elapsed from the last administration of study drug, even if the study has been closed.

Unrelated SAEs must be collected and reported during the study and for up to 30 days after the last dose of study medication.

SUSARs are reported to Investigators at each site and associated IRB/IEC when the following conditions occur:

- The event is an SAE
- There is reasonable possibility that the event is an adverse reaction caused by the administered drug
- The adverse reaction is unexpected, that is to say, not foreseen in the IB

Individual SUSARs considered to be a significant safety issues and/or which result in a change to the informed consent form will be reported in an expedited manner to all Investigators and IRB/IECs.

Reporting of any SAEs to applicable regulatory authorities will be the responsibility of the Local Sponsor in compliance with local regulations.

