10.4. Safety Analyses

Safety will be assessed through the summary of adverse events, serious adverse events, laboratory test results, ECG parameters, and vital signs. Safety analyses will include all subjects who receive at least one dose of either ESK-001 or placebo. Subjects will be analyzed according to the actual treatment received.

Patient deaths (if any) will be listed.

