2 STUDY OBJECTIVES AND ENDPOINTS

Objectives	Endpoints
Primary	

To compare the Psoriasis Area and Severity Index (PASI-75) between doses of ESK-001 and placebo after 12 weeks of treatment	
Proportion of patients with moderate to severe psoriasis achieving $\geq 75\%$ reduction in PASI score at 12 weeks between doses of ESK-001 and placebo
Secondary	

To assess the safety and tolerability of ESK-001 dose in moderate to severe psoriasis patients	
Incidence of treatment-emergent adverse events (TEAEs) and serious adverse events (SAEs)

To characterize the pharmacokinetics (PK) of ESK-001	
Plasma concentrations and PK parameters of ESK-001

To assess the response rate in static Physician's Global Assessment (sPGA) score after 12 weeks of treatment	
Proportion of patients achieving an sPGA score of "0" ("cleared") or "1" ("minimal") after 12 weeks of ESK-001 treatment compared with placebo

To assess the response rate in PASI-50, 90, and 100 score after 12 weeks of treatment	
Proportion of patients achieving PASI-50, 90, and 100 after 12 weeks of ESK-001 treatment compared with placebo

To compare the response rate in PASI-75 among ESK-001 treatments	
Proportion of patients achieving PASI-75 at 12 weeks compared among the ESK-001 treatments

To assess the effect on body surface area (%BSA) involved with psoriasis after 12 weeks of treatment	
Change from baseline in %BSA after 12 weeks of ESK-001 treatment compared with placebo

To assess the change in Dermatology Life Quality Index (DLQI)	
Change from baseline in DLQI at Week 12 in ESK-001 compared with placebo
Exploratory	

To assess the change in pruritus numerical rating scale (NRS) after 12 weeks of treatment	
Change from baseline in NRS score after 12 weeks of ESK-001 treatment compared with placebo

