8 SAFETY ANALYSES

All safety analyses will be performed on the Safety Analysis Population and will be presented by each treatment group and the combined active treatment. In general safety data will be presented by descriptive statistics only and by nominal visit (if applicable). Safety data collected on unscheduled visits will be presented in listings only.

The treatment emergent period is defined as first dose through the end of study for subjects who complete the full treatment period of 12 weeks. If a subject discontinues study drug early, then the treatment emergent period will be first dose through four weeks after last dose.

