8.1 Adverse Events

AEs will be coded to MedDRA version 25.0. AEs will be presented by SOC and PT, unless otherwise noted, in order of descending frequency on the overall total, and multiple occurrences of the same event in the same participant will be counted only once in the tables.

The following summaries of AEs will be provided:

- Overall summary of TEAEs
- All TEAEs
- Study drug related TEAE
- TEAEs by severity
- Grade 3 or higher TEAE
- Serious TEAEs (SAEs)
- Study drug-related SAEs
- TEAE leading to treatment discontinuation
- TEAE leading to death

By-subject listings of all AEs, SAEs, TEAEs leading to treatment discontinuation, TEAE leading to death will also be provided.

8.2 12-lead Electrocardiogram

12-lead electrocardiogram (ECG) data will be measured and read by local and central laboratory, and will be summarized for all subjects in the Safety Analysis Population.

8.2.1 *ECG Numeric Variables*

HR, PR, QRS, and Fridericia-corrected QT (QTcF) interval based on central ECG read and changes from baseline will be summarized by treatment group using descriptive statistics. The change from baseline of these ECG parameters at each time point will be listed for each subject.

8.2.2 *Categorical Analysis*

The number and percentage of subjects with maximum treatment-emergent post-dose QTcF values based on central ECG read in the following mutually exclusive categories will be summarized by treatment group: > 450 msec, > 480 msec, > 500 msec, > 520 msec, and > 550 msec. The number and percentage of subjects with maximum post-dose QTcF increase from baseline of > 30 msec and > 60 msec (mutually exclusive) will be summarized by treatment group.

Clinical significance will be summarized by treatment group and overall for the local and central ECG reads separately.

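### The safety endpoint names SAEs without a treatment-emergent limit, but the SAP's by-arm SAE table counts only serious TEAEs, so late SAEs in early stoppers who stay in follow-up are left out

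*SAP*

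**What the plan says.** SAP Section 2 repeats the protocol's secondary safety endpoint: "Incidence of treatment-emergent adverse events (TEAEs) and serious adverse events (SAEs"). The treatment-emergent qualifier is attached to the first item only. The endpoint gives no time window and does not mention deaths.

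SAP Section 8 runs the treatment-emergent period to end of study for patients who complete 12 weeks of treatment. For the others: "If a subject discontinues study drug early, then the treatment emergent period will be first dose through four weeks after last dose". SAP Section 8.1 labels its SAE summary "Serious TEAEs (SAEs"), and both its death summary and its dedicated death listing are confined to TEAEs. The same section includes a summary of study drug-related SAEs with no treatment-emergent label, and by-subject listings of all AEs and all SAEs.

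On follow-up after stopping drug, Protocol Section 7.2 says: "Patients who discontinue study drug should continue in the study to complete all scheduled assessments". Protocol Section 8.3.1.4 requires reporting of "Any AE that is serious and that occurs during the course of the study from the signing of the informed consent to end of study", and adds for related events: "Related SAEs must be collected and reported regardless of the time elapsed from the last administration of study drug". For unrelated events: "Unrelated SAEs must be collected and reported during the study and for up to 30 days after the last dose of study medication". On deaths, Protocol Section 10.4 says: "Patient deaths (if any) will be listed".

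**The concern.** If SAEs in the endpoint meant only serious TEAEs, naming them separately would add nothing. The natural reading is that SAEs are to be counted whether or not they are treatment-emergent. The SAP's SAE table does not do that for patients who stop drug early and remain in the study. Their later serious events are collected, and they stay in the Safety Analysis Population denominator, but those events do not reach the by-arm count. A reader of the study report would take that table as the result for the SAE part of the endpoint, and would have to search the listings to find what it leaves out.

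Deaths raise a related issue. The protocol promises a list of deaths with no window, whereas the SAP's dedicated death listing covers only fatal TEAEs.

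**Working it through.** **The plan's own figures.** The documents give no expected SAE rate, stopping rate or safety precision. The only design figure is the power for PASI-75. At 60% versus 10%, 35 per arm and two-sided 0.05, the stated power of at least 99% reproduces (99.8% by the normal approximation, 99.5% by exact Fisher). This point uses only the 35 per arm and 210 total from that calculation.

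**Inputs for the window.**
- End-of-study visit: Day 115 ± 3 (Schedule of Assessments). The Day 113 target in SAP Appendix B lies inside that range.
- Last on-site dose for completers: the Week 12 visit, Day 84.
- Treatment-emergent period for early stoppers: last dose + 28 days (SAP Section 8).
- The SAP defines the period but does not say how an event is assigned to it. I take it to be by onset date.

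**Formula.** Days of scheduled follow-up outside the tables = 115 − (last dose day + 28).

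| Last dose | Window ends | Days outside (± 3) | Share of Days 1–115 |
|---|---|---|---|
| Day 1 | Day 29 | 86 | 75% |
| Day 15 | Day 43 | 72 | 63% |
| Day 29 | Day 57 | 58 | 50% |
| Day 57 | Day 85 | 30 | 26% |

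For last dose days spread evenly over Days 1 to 83 (mean Day 42), the mean is 115 − (42 + 28) = 45 days. Completers have none outside, because their period runs to end of study.

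**Check on the post-dose windows.** Completers are counted for about 115 − 84 = 31 days after last dose, and early stoppers for 28. The 28 days are also 2 fewer than the 30-day provision for unrelated SAEs in Protocol Section 8.3.1.4.

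**Expected events outside the tables.** Assumptions, none from the documents: 5% to 20% of 210 patients stop early, all stay to Day 115, the mean gap is 45 days, and SAEs occur at 2 to 10 per 100 patient-years.

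- Low: 210 × 0.05 × (45/365.25) × 0.02 = 0.03
- High: 210 × 0.20 × (45/365.25) × 0.10 = 0.52

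The Poisson chance of at least one such event is 1 − e^(−0.03) ≈ 3% to 1 − e^(−0.52) ≈ 40%. An expectation near one needs harsher inputs. With 15% stopping and a 10% 16-week SAE risk, 210 × 0.15 × (45/115) × 0.10 = 1.2. That risk corresponds to 0.10 / (112/365.25), or about 33 SAEs per 100 patient-years. One patient in an arm of 35 is 1/35 = 2.9 percentage points.

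**The case against.** The best defence of the SAP is Protocol Section 10.4.1, which describes treatment-emergent AE tabulations and then says SAEs are handled in a similar way. That can be read as already limiting SAEs to treatment-emergent ones. It can equally refer to format, since the tabulation sentence itself speaks of adverse events without the qualifier. The ambiguity stands, and it is a reason to state the window.

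A reader might infer more than the documents support in four ways.

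- **That the endpoint itself covers all SAEs to end of study, related ones without limit, and deaths.** Those time frames are collection and reporting rules in Protocol Section 8.3.1.4. Deaths enter only through the analysis text in Section 10.4, which promises a list and not a by-arm table.
- **That the four-week cut applies to everyone.** It applies only to early stoppers.
- **That late events disappear, related ones included.** Late SAEs, fatal ones among them, remain in the by-subject SAE listing. The related-SAE summary has no treatment-emergent label, so exclusion there is possible but not shown.
- **That doses with more early stopping will look safer.** Post-dose windows are similar (28 versus about 31 days), and an SAE that causes a patient to stop is on treatment and is counted. Only events starting more than four weeks after stopping are affected.

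The four-week rule is also a reasonable exposure-based convention for TEAEs, and nothing here argues against it for that purpose.

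**Conclusion.** The concern holds as a mismatch between the stated endpoint and the table that reports it. For early stoppers who remain in follow-up, SAEs and fatal events starting more than four weeks after last dose fall outside the SAE and death tables, for up to 86 scheduled days, and are kept in listings. The window for related SAEs needs to be stated.

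The likely effect on counts is small: 0.03 to 0.5 events over all six arms, on assumed rates. The day counts assume that each such patient stays to Day 115. Protocol Section 7.2 lets those unwilling or unable to continue leave after an early termination visit, so the true gap would be smaller. A systematic distortion between doses is not established. The public copy of SAP Section 12 shows no text under its heading on changes from the protocol, and I draw no conclusion from that.

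**What to change.** Keep the four-week rule for TEAEs. In SAP Section 8.1:

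1. Add by-arm rows for all SAEs and for all study drug-related SAEs, with onset from first dose to the end of each subject's participation in this study and before any open-label extension dosing.
2. Split each row into events on drug or within four weeks of last dose, and later events.
3. List all deaths, as Protocol Section 10.4 says, in place of fatal TEAEs only.
4. Keep related SAEs reported after the end of participation in listings only. Reporting of these has no end date, and tabulating them could credit extension-period events to a randomised arm, placebo included.

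Stating the onset period in item 1 also settles the window for related SAEs. If the sponsor prefers to restrict the SAE table to TEAEs, SAP Section 12 should record that as a change.

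The cost is a few extra table rows from data already collected. Off-drug events will appear in an arm's SAE count, but the split keeps them visible as such.

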8.1 Adverse Events

AEs will be coded to MedDRA version 25.0. AEs will be presented by SOC and PT, unless otherwise noted, in order of descending frequency on the overall total, and multiple occurrences of the same event in the same participant will be counted only once in the tables.

The following summaries of AEs will be provided:

- Overall summary of TEAEs
- All TEAEs
- Study drug related TEAE
- TEAEs by severity
- Grade 3 or higher TEAE
- Serious TEAEs (SAEs)
- Study drug-related SAEs
- TEAE leading to treatment discontinuation
- TEAE leading to death

By-subject listings of all AEs, SAEs, TEAEs leading to treatment discontinuation, TEAE leading to death will also be provided.

8.2 12-lead Electrocardiogram

12-lead electrocardiogram (ECG) data will be measured and read by local and central laboratory, and will be summarized for all subjects in the Safety Analysis Population.

8.2.1 *ECG Numeric Variables*

HR, PR, QRS, and Fridericia-corrected QT (QTcF) interval based on central ECG read and changes from baseline will be summarized by treatment group using descriptive statistics. The change from baseline of these ECG parameters at each time point will be listed for each subject.

8.2.2 *Categorical Analysis*

The number and percentage of subjects with maximum treatment-emergent post-dose QTcF values based on central ECG read in the following mutually exclusive categories will be summarized by treatment group: > 450 msec, > 480 msec, > 500 msec, > 520 msec, and > 550 msec. The number and percentage of subjects with maximum post-dose QTcF increase from baseline of > 30 msec and > 60 msec (mutually exclusive) will be summarized by treatment group.

Clinical significance will be summarized by treatment group and overall for the local and central ECG reads separately.

8.3 Safety Laboratory Data

Safety laboratory data and change from baseline will be summarized by treatment group and visit using descriptive statistics.

Laboratory parameters that are graded in CTCAE Version 4.03 will be summarized by CTCAE grade. In the summary of laboratory parameters by CTCAE grade, for parameters with CTCAE grading in both high and low direction (e.g., calcium, glucose, magnesium, potassium, sodium), CTCAE in high and low directions will be summarized separately. Subjects with treatment-emergent laboratory abnormalities of Grade 3 or higher will also be summarized. Shift from baseline to the worst post-baseline CTC grade of Grade 3 or higher will also be presented for select laboratory tests of interest including neutrophils, platelets, hemoglobin, creatine kinase, AST, ALT, total bilirubin, triglycerides, and cholesterol.

Absolute values over time will also be plotted for select laboratory tests of interest including neutrophils, platelets, hemoglobin, creatine kinase, AST, ALT, total bilirubin, triglycerides, and cholesterol. Listings of laboratory values will be generated and the results that are out of the reference range will be flagged.

8.3.1 *Potential Drug-induced Liver Injury*

The liver function tests, namely alanine aminotransferase (ALT), aspartate aminotransferase (AST), alkaline phosphatase (ALP), and total bilirubin (TBL) are used to assess possible drug - induced liver injury (DILI).

A graph of distribution of peak values of ALT versus peak values of TBL will be presented. ALT and TBL values will be presented on a logarithmic scale. The graph will be divided into

4 quadrants with a vertical line corresponding to $3 \times$ the upper limit of normal (ULN) for ALT and a horizontal line corresponding to $2 \times$ ULN for TBL.

The number and percentage of subjects with elevated liver function tests (based on safety laboratory data) during the TEAE period will be summarized by categories of elevation ($>3 \times$ ULN, $> 5 \times$ ULN, $> 10 \times$ ULN, $> 20 \times$ ULN for ALT and AST, $> 1.5 \times$ ULN for ALP, and $> 1.5 \times$ ULN and $> 2 \times$ ULN for TBL), along with the following categories of normalization (i.e. return to $\leq 1 \times$ ULN, or return to baseline if baseline $>$ ULN): never normalized, normalized after permanent discontinuation of study drug, normalized during treatment period and elevated after permanent discontinuation of study drug. Potential Hy's law cases will be investigated by summarizing the number of subjects with elevated ALT or AST ($> 3 \times$ ULN), elevated ALP ($> 2 \times$ ULN) and elevated total bilirubin ($> 2 \times$ ULN) where transaminase elevation coincides with or precedes BILI elevation.

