2.5. Risk-Benefit Assessment

ESK-001 is being developed as an oral treatment for moderate to severe psoriasis. Based on the mechanism of action of ESK-001, the likelihood of benefit for patients enrolled in this study is expected to be high since substantial clinical efficacy has already been demonstrated by other molecules with the same mechanism of action, i.e., inhibition of TYK2 ([Papacharalambous et al., 2020](#); [Papp et al., 2018](#)). Furthermore, patients will be offered the opportunity to receive ESK-001 after they complete the study by enrolling in a long-term open label extension study.

Initial studies in healthy participants have demonstrated ESK-001 was tolerated well and had no safety findings of clinical concern. The nature and frequency of safety assessments in this study are guided by the safety profile of other TYK2 inhibitors being developed in psoriasis and the potential immunomodulatory effects of TYK2 inhibition. These inhibitors have been generally well tolerated and with an acceptable safety profile. Based on ESK-001's high specificity for TYK2, the safety concerns associated with JAK inhibition are considered to have been reduced. In addition, a safety monitoring committee will be convened, including a cardiologist, to oversee overall patient safety, including the potential for adverse events associated with JAK inhibition.

Taken together the overall benefit-risk assessment is favorable and supports this Phase 2 study in psoriasis patients with moderate to severe disease.

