8.3.1.2.2. Severity

The severity of an event describes the degree of impact upon the subject and/or the need for medical care necessary to treat the event. All clinical AEs encountered during the clinical study will be reported on the AE page of the eCRF. Severity of AEs will be graded based on a modified CTCAE, Version 5.0 and reported in detail as indicated on the eCRF. For any AEs not found in the CTCAE, a description of intensity grading can be found below:

Grade 1 - Mild	Asymptomatic or mild symptoms; clinical or diagnostic observations only; intervention not indicated.
Grade 2 - Moderate	Minimal, local or noninvasive intervention indicated; limiting age-appropriate instrumental activities of daily living.
Grade 3 - Severe	Medically significant but not immediately life-threatening; hospitalization or prolongation of hospitalization indicated; disabling; limiting self-care activities of daily living.
Grade 4 - Life-threatening	Life threatening consequences; urgent intervention indicated
Grade 5 – Death	Death related to AE

Any change in severity of a persistent AE will be captured by recording a new AE with the current severity and a start date of when the severity changed. The prior event will be updated with a stop date of when the severity changed. When changes in the severity of an AE occur more frequently than once a day, the maximum intensity for the event should be noted for that day.

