10.4.2. Laboratory Tests

Descriptive summaries of laboratory values, including changes from baseline and treatment-emergent abnormalities, will be generated. Shift tables reflecting changes from baseline (e.g., normal to low, high) will be presented for a subset of laboratory parameters.

The liver function tests, namely ALT, AST, ALP, and TBL, are used to assess possible drug-induced liver toxicity (DILI). A listing of liver function test results that meet DILI criteria will be generated.

10.4.3. 12-Lead Electrocardiogram

The RR, PR, QRS, and QT intervals will be measured and read by a central laboratory. HR will be calculated as $60 / (\text{RR} \times 1000)$ (with RR expressed in msec) and rounded to the nearest integer.

Correction for Heart Rate

Corrected QT interval (QTc) will be calculated using the manually over-read QT values. Each individual ECG QT value will be corrected for HR. The measured QT data will be corrected for HR using QTcF as per the following formulae/method (with QT, RR and QTc expressed in msec):

Fridericia's Correction:

$$QTcF = \frac{QT}{(RR / 1000)^{(1/3)}}$$

ECG Numeric Variables

HR, PR, QRS, and QTcF will be summarized using descriptive statistics. For each time point of measurement, the changes from baseline will be summarized using descriptive statistics.

Categorical Analysis

The incidence count and percentage of patients with any postdose QTcF values of >450 msec, >480 msec, and >500 msec will be tabulated. Patients with QTcF values >520 msec will be listed with corresponding baseline values, Δ QTcF, and baseline and treatment HR. The incidence count and percentage of patients with Δ QTcF increase from baseline of >30 msec and >60 msec will be tabulated.

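### SAP 8.3 limits its laboratory shift table and treatment-emergent summary to Grade 3 or higher, where Protocol 10.4.2 sets no grade floor, and its CTCAE version differs from the one used for adverse events

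*SAP*

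**What the plan says.** Protocol 10.4.2 makes two commitments on laboratory data. The first concerns levels and abnormalities: "Descriptive summaries of laboratory values, including changes from baseline and treatment-emergent abnormalities, will be generated". The second concerns movement within patients relative to their own starting value: "Shift tables reflecting changes from baseline (e.g., normal to low, high) will be presented for a subset of laboratory parameters". Neither carries a grade threshold.

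SAP 8.3 has a counterpart to each, and both are limited to Grade 3 or higher. The counterpart to the first commitment reads: "Subjects with treatment-emergent laboratory abnormalities of Grade 3 or higher will also be summarized". The counterpart to the second is the SAP's only shift table, and it names the tests it has in mind: "Shift from baseline to the worst post-baseline CTC grade of Grade 3 or higher will also be presented for select laboratory tests of interest".

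SAP 8.3 also contains outputs with no floor. Values and change from baseline are summarised by arm and visit, selected tests are plotted over time, and all values are listed with out-of-range flags. There is also a summary by grade: "Laboratory parameters that are graded in CTCAE Version 4.03 will be summarized by CTCAE grade". For parameters graded both ways, "CTCAE in high and low directions will be summarized separately". SAP 8.3.1 adds liver-test categories that start above 3 x ULN for ALT and AST and above 1.5 x ULN for ALP and total bilirubin.

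For adverse events, Protocol 8.3.1.2.2 uses another version of the criteria: "Severity of AEs will be graded based on a modified CTCAE, Version 5.0".

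**The concern.** The SAP narrows two planned safety displays, and the SAP text supplied gives no reason. Protocol Section 10 requires deviations from the planned analyses to be described and justified in the study report. (SAP Section 12, on changes from the protocol, shows a heading with no text beneath it. That may be a product of text extraction, so nothing here rests on it.)

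The protocol's own example is a move out of the normal range. A patient who makes that move and stops at Grade 1 or 2 enters neither the SAP's shift table nor its treatment-emergent summary. This is a five-dose study with safety as a secondary objective, and a count of newly worsened patients by arm is the natural way to look for a dose pattern. A table restricted to Grade 3 or higher may have too few entries to show one, and an empty table can be misread as reassurance.

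The version difference is a separate, smaller matter. A laboratory abnormality that is also recorded as an adverse event is graded under both versions, and no reason is given for using two.

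**Working it through.** The plan states no figure for this point, so there is nothing to reproduce. The check is a comparison of the texts, followed by a short illustration.

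**Step 1. What each planned output can show.**

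| Output (SAP 8.3, 8.3.1) | Covers changes below Grade 3 | Relative to baseline | Counts patients by arm |
|---|---|---|---|
| Values and change from baseline by visit | yes | yes | no |
| Summary by CTCAE grade | yes | not stated | yes |
| Treatment-emergent abnormalities | no | treatment-emergent; SAP 8 defines the period only | yes |
| Shift table, selected tests | no | yes | yes |
| Plots of absolute values, selected tests | yes | no | no |
| Flagged listings | yes | no | no |
| Liver categories | ALT/AST only above 3 x ULN; ALP and bilirubin above 1.5 x ULN | only in the normalisation rule | yes |

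No row is stated to do all three. The missing item is a count, by arm, of patients who newly worsened to a level below Grade 3. Tests without a CTCAE grade get no categorical summary, apart from out-of-range flags in the listings.

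**Step 2. Whether the by-grade summary fills the gap.** Protocol 5.3 excludes AST/ALT at or above 2 x ULN and haemoglobin below 9 g/dL. A patient can therefore enter with AST or ALT just under 2 x ULN, or haemoglobin at 9 g/dL. Take two patients whose worst ALT is just under 2 x ULN, one who entered at that level and one who entered normal. If the grade depends on the value alone, both fall in the same cell of a by-grade summary. Neither reaches a liver category, which starts above 3 x ULN. Change from baseline separates them only through its contribution to an arm-level statistic. The summary fills the gap only if it is baseline-relative, and SAP 8.3 does not say that it is.

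**Step 3. How informative a Grade 3+ table is.** Inputs: n = 35 per arm (SAP Section 4), and true rates p of Grade 3 or higher, which are assumptions because the documents give none. The probability that an arm has no such patient is (1 - p)^n.

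- p = 1%: 0.99^35 = 0.703; expected patients 35 x 0.01 = 0.35
- p = 2%: 0.98^35 = 0.493; expected 35 x 0.02 = 0.70
- p = 5%: 0.95^35 = 0.166; expected 35 x 0.05 = 1.75

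For the five active arms together, n = 5 x 35 = 175: 0.99^175 = 0.172 and 0.98^175 = 0.029.

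For comparison, assume 10% of patients newly worsen to Grade 1-2. The expected count is 35 x 0.10 = 3.5 per arm, with a probability of none of 0.90^35 = 0.025. Such changes would usually be countable in each arm, but no planned table is stated to count them as new.

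**Step 4. CTCAE versions.** SAP 8.3 names 4.03; Protocol 8.3.1.2.2 names a modified 5.0. Neither set of criteria, nor the modification, is in the documents. The difference is established; which tests it affects is not.

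**The case against.** The strongest reply is that a reader might infer that moderate dose-related changes are hidden, and that SAP 8.3 itself refutes this. The by-grade summary has no floor and separates high from low. Change from baseline is shown by arm and visit, and out-of-range values are flagged. SAP Section 8 presents all safety data for each arm and for combined active. This stands: moderate changes are visible by dose. What is missing is narrower, namely the baseline-relative count of patients below Grade 3.

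A second reply is that randomisation against placebo balances entry abnormalities in expectation. That is true, but balance at about 35 per arm is only approximate, and it does not turn a prevalence count into a count of new abnormalities.

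Third, the protocol promise is loose. It gives an example, speaks of a subset of parameters and leaves detailed methods to the SAP. This leaves the choice of tests and categories open. It does not readily cover removing every shift below Grade 3, and the sentence on treatment-emergent abnormalities has no such qualifier.

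Fourth, the single-arm probabilities are selective. At the same assumed rates, an empty table across all five active arms has probability only 17% or 3%. This also stands. The combined-active column would often show something, but it cannot show a pattern across doses.

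Two other strong readings are not supported. A reader might infer from the two CTCAE versions that the sets of grades cannot be compared. The documents identify no test that is graded differently. Moreover, Protocol 8.3.1.3 records only clinically significant abnormalities needing active management as adverse events, so the two tables would differ even under one version. A reader might also infer, because Protocol 2.5 cites "the potential immunomodulatory effects of TYK2 inhibition", that lymphocytes and immunoglobulins were wrongly left out of the shift table. The SAP's list of tests is introduced as non-exhaustive, and SAP Section 10 summarises T/B/NK cell counts by arm and visit, so that reading is not pursued.

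**Conclusion.** The point holds as a reporting gap that should be closed. SAP 8.3 restricts both the treatment-emergent summary and the only shift table to Grade 3 or higher, narrower than Protocol 10.4.2 and without a stated reason. No table is stated to count new worsening to Grade 1-2 or out of range, including ALT or AST rises that stay at or below 3 x ULN.

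The size depends on assumed event rates. If true Grade 3+ rates are 1% to 2%, a given arm's shift table is empty 70% to 49% of the time; at 5% this falls to about 17%. The textual finding does not depend on these rates. The CTCAE difference is real and unexplained. Its effect cannot be sized from the documents, and the most that can be said is that grades may not be comparable where the versions differ. No efficacy endpoint, sample size, power or alpha is affected.

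**What to change.** In SAP 8.3:

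1. Present shifts from baseline grade to worst post-baseline grade for all grades, by arm and for combined active, keeping Grade 3 or higher as a subset. For selected tests without a CTCAE grade, present low/normal/high shifts.
2. Summarise treatment-emergent laboratory abnormalities of any grade, and state that treatment-emergent means worsened from baseline.
3. Grade laboratory values by the CTCAE version used for adverse-event severity in Protocol 8.3.1.2.2, or state why two versions are used.

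If the Grade 3 floor is kept, record it as a departure from Protocol 10.4.2 and give the reason. The cost is SAP wording and a few more table rows. All the data are already collected.
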